2.2 Secondary objective

Additionally, this randomized double-blinded study will evaluate the efficacy of intravenous immunoglobulin (NewGam 10%) in patients with a-MCI over 36 months, 48 months, and 60 months after the first infusion.

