2.3 Primary endpoint

- Change in ventricular volumetric as measured by MRI at baseline, 24 months, 36 months, 48 months, and 60 months following the first infusion of either 0.4 g/kg NewGam or 0.9% saline solution (placebo) every 14 days x 5.

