3.3 Estimated study duration

The duration of each study subject is approximately 24 months, including one screening visit over a period of approximately 28 days, 5 days of infusions over a 2-month period of time, and follow-up visits at 4, 8, 12, 16, 20, and 24 months after the first infusion. Subjects will be given the option to continue study follow-up visits at 36, 48, and 60 months after the first infusion.

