 1. HIV-I & II, HCV, HBV, B19, HAV
 2. Adverse events and Concomitant Meds
- Complete all Visit 9 study activities described above
- Subjects will not attend Visit 10 and Visit 11
- Complete all Visit 12 study activities
- Complete all Visit 13, 14, and 15 study activities (optional)

Patients who convert to Alzheimer Disease will be followed for safety reasons, to determine rate of conversion between groups, and to track any continued changes in ventricular volume between the 0.4 g/kg NewGam or 0.9% saline solution (placebo) groups.

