15.0 STATISTICAL ANALYSIS

15.1 Primary endpoint

The aim of the primary efficacy analysis is to demonstrate an advantage for subjects treated with IVIG over subjects treated with placebo at the end of the study as measured by change in ventricular volume. The primary efficacy analyses will be performed on the intent-to-treat (ITT) population. The ITT population is defined as all subjects who were randomized, received three or more infusions, and had a brain MRI at baseline and at 24 months.

Annualized percent change in total ventricular volume (APCV) is the primary biomarker of interest. Brain MRI will be obtained at baseline, 12 months, 24 months, 36 months, 48 months, and 60 months. Differences between the IVIG and placebo group at month 12, 24, 36, 48, and 60 will be analyzed using a 2 x 2 analysis of variance. Participants will also be classified as early MCI (EMCI) if baseline CDR-SB is less than 1.5, and late MCI (LMCI) if CDR-SB is greater than or equal to 1.5.

Treatment (IVIG, placebo), MCI status (EMCI, LMCI), and the treatment X MCI status interaction will be included in the model. If the interaction is statistically significant ($p < 0.05$), MCI status will be stratified and differences in APCV between the groups compared within each stratum.

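### Section 15.1 tests each MRI visit on its own, so the optional month 36–60 comparisons rest on self-selected subjects and make no use of decliners' earlier scans

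*Combined protocol and SAP*

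**What the plan says.** Section 15.1 sets the MRI outcome: "Annualized percent change in total ventricular volume (APCV) is the primary biomarker of interest". Arm differences in it "at month 12, 24, 36, 48, and 60 will be analyzed using a 2 x 2 analysis of variance". The model is then listed: "Treatment (IVIG, placebo), MCI status (EMCI, LMCI), and the treatment X MCI status interaction will be included in the model". No visit term, subject term or method for missing scans is given. The analysis set is "all subjects who were randomized, received three or more infusions, and had a brain MRI at baseline and at 24 months"; nothing is required of months 36–60.

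On those later visits Section 3.3 states: "Subjects will be given the option to continue study follow-up visits at 36, 48, and 60 months after the first infusion". Section 8.0 marks the same visits optional for subjects who have converted to AD. Under Section 6.5, subjects who decline the extension can be unblinded if they ask, while those who continue may be unblinded at month 60.

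The later visits still matter to the plan. Section 2.2 makes efficacy "in patients with a-MCI over 36 months, 48 months, and 60 months after the first infusion" the secondary objective, and Section 2.3 gives the primary endpoint as "Change in ventricular volumetric as measured by MRI at baseline, 24 months, 36 months, 48 months, and 60 months following the first infusion".

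For cognition, Section 15.2.2 plans mixed-effects models on every available observation. The MRI outcome has no counterpart.

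**The concern.** A visit-by-visit ANOVA at month 36, 48 or 60 compares only those who chose to go on. It estimates the treatment difference in the whole analysis set only if that choice is unrelated to ventricular change, or related in a way that cancels between arms. The plan holds the information that would help, namely each decliner's month 12 and 24 scans, but does not use it at the later visits.

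A link between progression and continuing is plausible. Experimental drugs are barred during the study (Section 6.11.1), and Amendment 9 explains that subjects may want to enter other MCI or AD trials. A subject who is getting worse therefore has a reason to decline. At stake are the estimates for the secondary objective and the later time points of the primary endpoint.

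**Working it through.** **1. Reading the model.** A 2 x 2 ANOVA has two two-level factors. Section 15.1 names both (treatment, MCI status), and neither is visit. The plan does not use the word separate, but one test per visit is a firm inference.

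**2. The plan's own figure.** Section 16.0 gives 82% power for 120 units, 25 per group, two-sided 0.05, and no SD, so it cannot be reproduced directly. Solving the noncentral t (noncentrality d√(n/2), df 2n − 2) for 82% at n = 25 gives d = 0.83, that is SD = 120/0.83 ≈ 145 units. The figure is for mean ventricular volume at month 26, not for APCV at an extension visit; d = 0.83 is borrowed below only as an assumed effect. Holding d there, power by number scanned per arm is:

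| Scanned per arm | 25 | 20 | 15 | 12 |
|---|---|---|---|---|
| Power | 82% | 73% | 59% | 49% |

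The documents give no retention rate, so this is a range and not a forecast.

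**3. Precision when joining is random.** Let r be the share scanned at month 60 and ρ the correlation of APCV between months 24 and 60.
- Continuers only: variance of an arm mean = σ²/(nr).
- Adding b × (month-24 mean of the whole arm − month-24 mean of continuers): about σ²[(1 − ρ²)/(nr) + ρ²/n].
- Ratio = 1 − ρ²(1 − r).

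For ρ = 0.8 and r = 0.6 this is 1 − 0.64 × 0.4 = 0.744. Over a range: r = 0.8, ρ = 0.8 gives 0.872; r = 0.6, ρ = 0.6 gives 0.856; r = 0.6, ρ = 0.9 gives 0.676. A simulation at the first setting (25 per arm, 6000 runs) gave SE 0.372 against 0.319, and 0.319²/0.372² = 0.735.

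A second simulation used all scans. Its assumptions were 25 per arm, log-volume growth of 11% against 6.5% a year (near the 12.3% and 6.7% cited in Section 1.0), subject-slope SD 4%, scan SD 2%, about 70% joining, and known covariance. The visit-wise SD was 1.35–1.38 points a year against 1.16 for the mixed model. 1.16²/1.35² = 0.74 and 1.16²/1.375² = 0.71, so 26–29% less variance.

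**4. Bias when joining depends on month-24 change.** The first two rows come from the second simulation; ranges span repeat runs. In the strong case one run kept about 13 placebo and 19 IVIG subjects, (13 + 19)/50 = 64%. The other rows come from the two-visit simulation with r = 0.6 and ρ = 0.8. It has treatment as its only factor, and the log-odds of joining fall by 1 per SD of month-24 APCV wherever selection acts.

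| Scenario | True benefit | Visit-wise | With earlier scans |
|---|---|---|---|
| Moderate selection | 4.5 points/yr | 4.2–4.3 | 4.5 |
| Strong selection | 4.5 points/yr | 3.4–3.7 | 4.5 |
| Same rule in both arms | 0.83 SD | 0.73 | 0.83 |
| Selection in placebo only | 0.83 SD | 0.51 | 0.83 |
| No effect, same rule | 0 | 0.00 (type I error 4.9%) | 0.00 |
| No effect, placebo only | 0 | −0.28 (type I error 11.4%) | about 0 |

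The first two rows are attenuations of 0.2–0.3 in 4.5 (4–7%) and 0.8–1.1 in 4.5 (18–24%).

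The last row can be checked by hand. The visit-wise bias equals ρ times the month-24 shift among placebo continuers, and the simulated biases at ρ = 0.6, 0.8 and 0.9 give 0.210/0.6, 0.283/0.8 and 0.311/0.9, all about 0.35 SD. Type I error was 9.0%, 11.4% and 13.5% at those correlations, and 7.6% at 80% retention with ρ = 0.8. The false signal here runs against IVIG; the mirror case, selection in IVIG only, would favour it.

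**The case against.** The strongest reply is that the trial's decision point is month 24. Section 2.1 sets the primary objective there, and Section 17.0 calls the study exploratory, with next steps judged at two years. Optional extension visits cannot alter that comparison. Section 7.13 asks for every attempt to follow subjects to Visit 15, and Section 8.0 keeps converters partly to track ventricular volume. All of this stands, and it limits the point to months 36–60.

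The sizes are also open to challenge. Slope SD, scan SD, joining rate and strength of selection are assumed. The growth rates are borrowed from mild to moderate AD, whereas this trial enrols a-MCI and excludes moderate or severe atrophy. Moderate selection moves the estimate by 0.3/1.37, about a fifth of a standard error. The mixed model was given the true covariance; estimating it would likely shrink the gain.

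Several stronger readings are tempting but unsupported:
- A reader might infer that the extension results must be biased toward no effect. That needs a working drug and faster progressors declining; the documents show neither.
- A reader might infer that the analysis takes anyone scanned, or throws earlier scans away. It is confined to the 15.1 set, the month 12 and 24 scans are analysed at their own visits, and the baseline scan enters every APCV.
- A reader might infer that converters are singled out. The visits are optional for everyone.
- A reader might infer that the unblinding rule itself makes opt-in differ by arm. As written it applies after a subject declines, so it is an incentive to leave in both arms.

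**Conclusion.** The point holds for months 36, 48 and 60 only. There the plan compares self-selected subjects and leaves decliners' month 12 and 24 scans unused, although Section 15.2.2 already takes the better route for cognition.

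The loss of precision arises even with random joining: about 26–29% of the variance is avoidable on the assumed inputs with known covariance, and less with weaker correlation, higher retention or an estimated covariance. The bias is conditional in size and direction. It attenuates a real effect if faster progressors decline, vanishes with no effect and a common opt-in rule, and takes type I error to about 8–14% in the scenarios where the rule differs by arm. The documents give no retention figure, so the harmful cases can be neither confirmed nor excluded.

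**What to change.** In Section 15.1, for months 36, 48 and 60, replace the visit-wise tests with one linear mixed model:
- **Data:** log ventricular volume at all scheduled post-baseline scans of the 15.1 analysis set, including subjects who declined the extension.
- **Terms:** treatment, visit, treatment x visit, MCI status, treatment x MCI status and log baseline volume. The wording of 15.2.2 cannot simply be copied, because it also lists no visit term. State how the existing rule for a significant interaction carries over.
- **Covariance:** unstructured by scheduled visit (five visits, 5 × 6/2 = 15 parameters) with a pre-specified simpler fallback, and Kenward-Roger degrees of freedom.
- **Alternative:** a continuous-time random-slope model if actual scan dates or early-termination scans are to be used. Appendix C implies such scans through its shared M24/ET and M60/ET columns, but Section 7.13 lists no MRI. Early-termination scans of subjects without a month-24 MRI would also widen the analysis set, which would need to be stated.
- **Reporting:** contrasts back-transformed to annual percent change; numbers scanned and baseline and month-24 characteristics of continuers and decliners by arm; a missing-not-at-random sensitivity analysis.

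The month-24 ANOVA can stay as planned if the sponsor prefers. The visit-wise extension ANOVAs become descriptive.

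The cost is SAP wording and modest extra analysis, with no new data. The downside is that results rest on data missing at random given earlier scans, and on a covariance choice.

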3.0 STUDY PLAN

3.1 Study design

This is a single center, randomized, double blind, placebo controlled, parallel-group, out-patient study in male and female subjects aged 50 to 84 years with amnesic-mild cognitive impairment. Subjects will be randomized to receive either an infusion of IVIG at 0.4 g/kg or 0.9% saline solution (placebo) every 14 days for two months for a total of five infusions.

Fifty subjects will be enrolled and randomized in a 1:1 IVIG 2.0 g/kg: placebo ratio. Twenty-five subjects will receive IVIG and 25 subjects will receive placebo.

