4.1 Inclusion criteria

1. Signed and dated written informed consent obtained from the subject in accordance with the local regulations. The subject's collaborative informant must also consent to participate in the study.
2. Age from 50 to <85 years.

3. Diagnosis of Mild Cognitive Impairment, Amnesic type (single or multi domain) according to Petersen criteria (Appendix B), NIA diagnostic guidelines, [15] and supported by a CDR score of 0.5.
4. Mini-Mental State Examination (MMSE) score of 24-30, inclusive.
5. Rosen Modified Hachinski Ischemic score ≤ 4 .
6. Willing to consent to ApoE testing and agree to disclose ApoE4 status. Previous ApoE testing will be accepted.
7. Receiving stable doses of medication(s) for the treatment of non-excluded medical condition(s) for at least 30 days prior to screening.
8. Agree to refrain from taking any medication, vitamin, or herbal supplement indicated for a-MCI or AD or considered to enhance cognition unless approved by the investigator for the duration of the study.
9. Ability to attend all clinical visits and have an informant capable of accompanying the subject on specific clinic visits for two years or the duration of the study.
10. The subject's collaborative informant (support person) must be someone who has known the subject for at least 4 years; agrees to have at least 2 separate communications with the study participant per month for the duration of the study (one of these communications must be in person); and attends and completes the CDR interview at 8 study visits along with the subject.
11. Fluency in English and evidence of adequate premorbid intellectual functioning.
12. Adequate manual dexterity, visual, and auditory abilities to perform all aspects of the cognitive and functional assessments.
13. Venous access suitable for repeated infusion and phlebotomy.
14. In the opinion of the investigator, the subject and informant will be compliant and have a high probability of completing the study, including all scheduled evaluations and required tests.

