15.2 Secondary Endpoints

15.2.1 Conversion to AD

Conversion to AD is measured by NINCDS-ADRDA and NIA [14] criteria for diagnosis of Alzheimer Disease and Clinical Dementia Rating (CDR) (Appendix A).

Kaplan-Meier survival curves will be estimated and will plot the proportion of treatment and control subjects who remain without a diagnosis of AD at month 24, 36, 48, and 60. The log-rank test will be used to determine whether the survival curves are different for the two groups of subjects. Cox proportional hazards will be used to assess the incidence of AD in treatment versus control subjects adjusting for age and sex.

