16.0 SAMPLE SIZE AND POWER FOR PRIMARY ENDPOINT

Twenty-five subjects will be randomized to placebo and 25 subjects will be randomized to the group receiving IVIG. Twenty-five subjects in each group provides 82% power to detect a 120 unit difference in mean ventricular volume between the groups at month 26. This calculation is based on a two-sided test with alpha set at 0.05.

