30.0 AMENDMENT 6: SUMMARY OF CHANGES

30.1 Introduction:

Amendment 6 consists of changes in the measurement of the primary endpoint and statistical analysis plan in sections 15.1 and 15.2

30.2 Rationale:

Since the study was designed and initiated, research from the Alzheimer's Disease Neuroimaging Initiative (ADNI) and others have utilized a sub-classification of early MCI (EMCI) and late MCI (LMCI) to improve the understanding of effects of interventions which may be unique to particular early stages in the progression of AD. Based on those studies, and using the cognitive data available in this study, participants were classified as EMCI if baseline CDR-SB was less than or equal to 1.5 and LMCI if CDR-SB was greater than 1.5.

This amendment includes the change of primary endpoint from ventricular volume to annualized percent change in ventricular volume. The amendment also reflects the change in the statistical analysis to include early and late MCI as study factors for all endpoints.

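### The primary APCV model leaves out age and baseline ventricular volume, both available for every analysed subject; the power effect is unknown, about -2 to +10 points for R2 from 0 to 0.30

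*Combined protocol and SAP*

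**What the plan says.** Section 15.1 names APCV as the primary biomarker and compares the arms with a 2 x 2 ANOVA. Its terms are given in full: "Treatment (IVIG, placebo), MCI status (EMCI, LMCI), and the treatment X MCI status interaction will be included in the model". MCI status is a two-level split of baseline CDR-SB at 1.5. No continuous covariate is listed, and no sensitivity analysis adds one.

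Both candidate covariates are in hand. Age is inclusion criterion 2 (50 to under 85). Ventricular volume is taken from the screening MRI (7.1). The analysis set in 15.1 requires MRI at baseline and at month 24, and baseline volume is the denominator of APCV.

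The secondary analyses adjust. For conversion (15.2.1): "Cox proportional hazards will be used to assess the incidence of AD in treatment versus control subjects adjusting for age and sex". The cognitive models in 15.2.2 carry the baseline score of each test as a continuous covariate.

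As background only: the amendment log shows that the superseded primary model was an ANCOVA on baseline volume. Amendment 6 records the "change of primary endpoint from ventricular volume to annualized percent change in ventricular volume" and explains the MCI factor. It does not say why no continuous covariate was kept.

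**The concern.** The primary comparison is small. Section 3.1 says: "Twenty-five subjects will receive IVIG and 25 subjects will receive placebo". In a trial of this size, two things depend on the baseline terms in the model.

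The first is residual variance. If age or baseline volume predicts APCV, that variation stays in the error term of the planned ANOVA.

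The second is chance imbalance. If the arms differ by chance on a predictive variable, the unadjusted contrast carries that difference. The ANOVA can correct only for imbalance on the CDR-SB split.

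The primary endpoint is thus the only one of the three modelled outcomes with neither age nor its own baseline value as a covariate, and 15.1 gives no reason.

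**Working it through.** **1. The plan's own figure.** Section 16.0 claims "82% power to detect a 120 unit difference in mean ventricular volume between the groups at month 26", and adds: "This calculation is based on a two-sided test with alpha set at 0.05". It states no SD, so the 82% cannot be reproduced; it can only be solved backwards.

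- Normal approximation: power = Phi(d x sqrt(n/2) - 1.96), with n = 25. Power 0.82 needs d = 0.813, so SD = 120/0.813 = about 147.6.
- Noncentral t, 48 df: d = 0.830, so SD = 120/0.830 = about 144.6.

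I use d = 0.83. It belongs to mean ventricular volume at month 26. Applying it to APCV at month 24 is an assumption, since the plan has no power figure for the model in 15.1.

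**2. The planned ANOVA.** With N = 50 and four cells, residual df = 50 - 4 = 46. The noncentrality is 0.83 x sqrt(25/2) = 2.93, and power is 81.9%.

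**3. Adding two covariates.** Let R2 be the share of within-cell APCV variance that age and log baseline volume explain together. The documents do not give it; I let it run from 0 to 0.30. Three things change:

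- Error variance is multiplied by (1 - R2).
- Residual df fall from 46 to 44. Alone, this costs less than 0.1 point of power.
- Estimating two slopes under expected chance imbalance inflates the variance of the contrast by about 1 + 2/(50 - 4 - 2 - 1) = 1 + 2/43 = 1.047.

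The noncentrality becomes 2.93 / sqrt((1 - R2) x 1.047).

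| R2 (assumed) | SE ratio, imbalance counted | Power, imbalance ignored | Power, imbalance counted | Change from 81.9% |
|---|---|---|---|---|
| 0 | 1.023 | 81.9% | 80.1% | -1.8 |
| 0.05 | 0.997 | 83.8% | 82.1% | +0.2 |
| 0.10 | 0.970 | 85.7% | 84.1% | +2.2 |
| 0.20 | 0.915 | 89.4% | 88.0% | +6.1 |
| 0.30 | 0.856 | 92.9% | 91.8% | +9.9 |

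For the SE, break-even is where (1 - R2) x 1.047 = 1, so R2 = 0.047/1.047 = 0.045. With the lost df it is about 0.05. Simulating both models with a random MCI split gives the same changes to within about half a point.

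**4. Fewer analysed subjects.** The analysis set needs at least three infusions and a month-24 MRI, so it may fall below 50. With 20 per arm, power is 72.4% unadjusted. Adjusted, with imbalance counted, it is 69.7% at R2 = 0, 74.2% at 0.10 and 79.1% at 0.20. The pattern is the same, with a slightly larger loss at R2 = 0 (72.4 - 69.7 = 2.7 points).

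**5. Size of chance imbalance.** Under simple 1:1 randomisation the standardised difference between arms in one covariate has SD sqrt(2/25) = 0.28. A gap above 0.5 SD arises in about 1 trial in 13. If that covariate has R2 = 0.20, a one-SD imbalance moves the unadjusted contrast by sqrt(0.20) x 0.28 = 0.13 SD, which is 0.13/0.83 = about 15% of the assumed effect.

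**The case against.** The strongest reply is that an unadjusted comparison of randomised arms is valid. Its type I error is not inflated by chance imbalance, and the study calls itself exploratory. That stands. A reader might infer that the planned ANOVA is biased or invalid; it is neither.

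A reader might also infer that the plan gives up precision it could have at no cost. The documents do not support this. They report no R2, part of what the covariates carry may already be in the MCI factor, and below about R2 = 0.05 adjustment gains nothing on average. The fix is free in data collection, not in power.

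The 0.83 SD is borrowed. Section 16.0 still speaks of volume, for which the earlier model was an ANCOVA, so its undisclosed SD may already be covariate-adjusted. This stands and limits the power figures to illustration.

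APCV already divides by baseline volume. This answers only part of the point. Division removes dependence on baseline only if change is exactly proportional to it, and it does nothing about age. How much dependence remains is unknown.

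Three further inferences go too far:

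- The Cox model shows that the plan adjusts AD conversion for age and sex. It does not show that age predicts ventricular change.
- Section 5.1 describes no stratification, but it does not exclude it.
- ApoE status is collected ("Willing to consent to ApoE testing and agree to disclose ApoE4 status"), but that alone does not make it a needed covariate. An optional third covariate would add analyst discretion.

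**Conclusion.** The point holds as a low-cost improvement, not as an error. Section 15.1 omits two baseline variables available for every analysed subject, and the plan adjusts its secondary outcomes without saying why the primary one differs.

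The effect on power is about -2 points at R2 = 0, none at 0.05, and about +2, +6 and +10 at 0.10, 0.20 and 0.30. This rests on an assumed R2, on an effect of 0.83 SD carried over from mean volume to APCV, and on 25 analysed per arm; it is less certain with fewer. The possible loss is small and bounded, while the possible gain is larger and comes with protection against chance imbalance in these two variables. That balance favours prespecifying them, or stating why not.

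A reader might infer from the amendment log that a covariate was dropped by mistake. The log describes superseded text and is silent on the reason, so it shows no mistake.

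**What to change.** In 15.1, replace the 2 x 2 ANOVA by an ANCOVA on APCV with treatment, MCI status, their interaction, age (continuous) and log baseline total ventricular volume (continuous). Fix both covariates before month-24 results are seen by arm. If those results have already been seen by arm, keep the ANOVA as primary and report the ANCOVA as a labelled sensitivity analysis. The documents do not settle which case applies: the rationale for Amendment 8 cites conversions in years 1 and 2 by MCI status, but not by treatment. The plan should therefore state it.

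Leave ApoE4 out of the primary model, and add no parallel log-volume analysis.

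The cost is one sentence in 15.1, no new data, two residual degrees of freedom, and up to about 2 points of power with 25 analysed per arm if the covariates prove not to be prognostic.
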